CCMO	Central Committee on Research Involving Human Subjects; in Dutch: Centrale Commissie Mensgebonden Onderzoek
CV	Curriculum Vitae
DSMB	Data Safety Monitoring Board
EU	European Union
EudraCT	European drug regulatory affairs Clinical Trials
GCP	Good Clinical Practice
IB	Investigator's Brochure
IC	Informed Consent
IMP	Investigational Medicinal Product
IMPD	Investigational Medicinal Product Dossier
METC	Medical research ethics committee (MREC); in Dutch: medisch ethische toetsing commissie (METC)
(S)AE	(Serious) Adverse Event
SPC	Summary of Product Characteristics (in Dutch: officiële productinfomatie IB1-tekst)
Sponsor	The sponsor is the party that commissions the organisation or performance of the research, for example a pharmaceutical company, academic hospital, scientific organisation or investigator. A party

that provides funding for a study but does not commission it is not regarded as the sponsor, but referred to as a subsidising party.

SUSAR Suspected Unexpected Serious Adverse Reaction

Wbp Personal Data Protection Act (in Dutch: Wet Bescherming Persoonsgevens)

WMO Medical Research Involving Human Subjects Act (in Dutch: Wet Medisch-wetenschappelijk Onderzoek met Mensen)

SUMMARY

Rationale: Painful polyneuropathy is a common condition that is difficult to diagnose and treat and has a negative impact on quality of life. Painful polyneuropathy is caused by degeneration of thin nerve fibers. With the current techniques, the diagnosis of thin fiber neuropathy can not be reliably established. Flavoprotein imaging is an optical method with which, among other things, pain transmission in the spinal cord can be measured. Because the epidermis or epidermis also contains a high density of pain nerve fibers, our hypothesis is that flavoprotein imaging is suitable for diagnosing thin fiber neuropathy.

Objective: In order to study whether painful neuropathy can be diagnosed with flavoprotein imaging, first of all a pilot study is needed, with which we want to investigate whether a reproducible and validated flavoprotein signal can be obtained at the middle finger tip of healthy subjects.

Study design:

- studying whether there is a time relationship between administering an electrical stimulus by means of finger electrodes and an optical (flavoprotein) signal on the fingertip of test subjects
- studying whether there is a linear relationship between the strength of the applied electrical signal and the size of the optical (flavoprotein) signal
- studying whether the signal is specific to the flavoprotein wavelength, by changing the filter settings of the camera
- studying whether the optical (flavoprotein) signal can be blocked by administering lidocaine / prilocaine cream on the fingertip
- studying whether the optical (flavoprotein) signal can be blocked by administering a capsaicin 8% patch on the fingertip

Study population: 10 healthy volunteers

Intervention (if applicable): the intervention with lidocaine / prilocaine cream and with capsaicin 8% patches is not the aim of the study, but serves as a negative control.

Main study parameters/endpoints:

- magnitude and time course of the flavoprotein response
- linearity of the electrical stimulation with the flavoprotein response
- block of the flavoprotein response by lidocaine / prilocaine creme and capsaicin patches

Nature and extent of the burden and risks associated with participation, benefit and group relatedness:

- time tax 45 minutes per person

-Discomfort: short-term painful electrical stimulation, about 3 hours of deafness of the index finger tip, about 3 days of hypersensitivity to pressure and temperature of the middle finger tip

-risk: none

1. INTRODUCTION AND RATIONALE

Painful polyneuropathy is a form of neuropathic pain that occurs when thin A δ or C nerve fibers become damaged. The exact incidence and prevalence of painful polyneuropathy is not known, but it is estimated that painful neuropathy occurs in 5% of the general population (1). Painful polyneuropathy has a negative influence on quality of life (2, 3) and is difficult to treat. The prevalence of untreatable neuropathic pain is estimated at 1.5% of the general population (4).

Painful polyneuropathy often presents itself as painful, burning or tingling feet. Painful, burning or tingling feet, however, can also be caused by narrowing of small arteries, venous insufficiency, osteoarthritis or rheumatoid arthritis of the foot joints, skin diseases such as a fungal infection or hives, or a marrow fracture, in addition to polyneuropathy. For the treatment of painful feet it is important to determine exactly what the underlying cause is. A problem here is that the aforementioned nerve fibers responsible for a painful polyneuropathy are difficult to investigate in neurological research or with additional examinations (5). With additional investigations are meant here:

- New guidance research / electromyography: this method mainly examines thick or A β sensitive nerve fibers and these are generally not at all or only slightly affected by a painful polyneuropathy
- Quantitative Sensory Testing: this allows sensitivity to temperature and strong mechanical stimuli to be investigated. This research is precise, but subjective. This means that the result is influenced by the concentration and pain experience of the test subject. In addition, the research is very labor-intensive.

Skin biopsies: in skin biopsies of the painful area, endings of epidermal nociceptors can be visualized and quantified by means of immunohistochemistry with the marker substance PGP9.5. Although this method is not 100% sensitive, it is often used as a gold standard for the diagnosis of painful, thin-fiber neuropathy. A disadvantage is that this method is not routinely available in hospitals and that it is very labor-intensive. A result can take 1-2 months.

- Videothermography / pulsed transit time / laser doppler. This method makes use of the fact that thin nerve fibers also regulate peripheral blood flow in addition to pain. This is an indirect measure of painful, thin-fiber neuropathy, of which the suitability for diagnosing painful, thin-fiber neuropathy is currently being investigated.

Because of the above, there is a need for a reliable, rapid and non-invasive method with which the function of thin nerve fibers can be measured. Autofluorescent flavoprotein imaging is a promising new technique for this. Autofluorescent flavoprotein imaging (AFI) is an optical technique that makes use of the property that certain endogenous mitochondrial

proteins, called under blue light, emit a green fluorescent signal in oxidized, or activated, state. Because nerve cells and their endings are very active, for generating the action potentials that are required for signal transmission, a lot of energy is required, AFI can be used to measure the degree of activation of such a nerve cell (6). Our research group has already demonstrated in experimental animals that this method is extremely suitable for studying nociceptive transmission in the spinal cord (Figure 1) (7). As in the spinal cord, there is also a high density of nociceptor endings in the epidermis (figure 2). These endings contain a high density mitochondria (figure 3) (8). Because there is a strong reduction in the number of nociceptor ends in the epidermis (Figure 4) (9) in neuropathy, it can be expected that the AFI signal after a nociceptive stimulus in the epidermis of people with a painful polyneuropathy is also greatly reduced. Thus, AFI could be used in the objectification of a painful, thin-fiber neuropathy.

This research application concerns a pilot study, with which we want to examine in healthy volunteers whether a reproducible and reliable AFI signal can be obtained after nociceptive stimulation in the epidermis.

[figure not shown]

Figure 1: autofluorescent flavoprotein imaging of the spinal cord of the rat, after nociceptive electrical stimulation of the left n. sciatic, for 0-10 seconds. Clearly visible is an increase in the AFI signal especially on the left side (= upper side in the figure), which decreases again after stopping the stimulus.

Figure 2: high density of nociceptor endings in the epidermis, demonstrated by immunohistochemical staining with PGP9.5. The endings have a somewhat "variceus" aspect. In these thickenings there is a high concentration of mitochondria (see figure 3).

Figure 3: electron microscopic recording of an axon terminal (A) and Schwann cell (SC) of a nociceptor termination. The arrow shows 11 mitochondria in this ending.

Figure 4: sharp decrease in the number of epidermal nociceptor endings in an animal model for neuropathy. sham = control animal, CCI = animal with chronic constriction injury (model

for neuropathy), u.dermis is upper dermis. The arrowheads show PGP9.5 labeled epidermal nociceptor endings, which are completely absent in the epidermis in the animal with neuropathy.

OBJECTIVES

Primary Objective:

To study whether painful neuropathy can be measured with flavoprotein imaging, first of all a pilot study is needed, with which we want to investigate whether a reproducible and validated flavoprotein signal can be obtained at the second fingertip of healthy subjects.

STUDY DESIGN

- studying whether there is a time relationship between administering an electrical stimulus by means of finger electrodes and an optical (flavoprotein) signal on the fingertip of test subjects
- studying whether there is a linear relationship between the strength of the applied electrical signal and the size of the optical (flavoprotein) signal
- studying whether the signal is specific to the flavoprotein wavelength, by changing the filter settings of the camera
- studying whether the optical (flavoprotein) signal can be blocked by administering lidocaine / prilocaine cream on the fingertip
- studying whether the optical (flavoprotein) signal can be blocked by administering a capsaicin 8% patch on the fingertip.

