5.9 Study parameters/endpoints

5.9.1 Main study parameter/endpoint

- magnitude and time course of the flavoprotein response
- linearity of the electrical stimulation with the flavoprotein response
- block of the flavoprotein response by lidocaine / prilocaine cream and 8% capsaicin patches

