5.11 Study procedures

- 1) Each subject will undergo a series of electrical stimuli (5Hz, for 10 seconds) with AFI measurement. Each stimulus strength (0.5, 0.6, 0.7, 0.8, 0.9 and 1.0 mA) will be administered twice. The stimulus is interrupted when the pain intensity exceeds 7. Thereafter, a (non-painful) 2000Hz, 1.0mA stimulus will be administered as a (negative) control for 10 seconds. The stimuli are administered by a Neurometer, a validated before (11). The middle finger is illuminated with a white light source, from which blue light with a wavelength of 480nm is filtered. This light excites oxidized flavoproteins. The signal is picked up by a digital camera that is connected to an upright microsoop. The stimulation and measurements take 15 minutes.

- 2) At the end of the above measurements, the middle finger tip is smeared with lidocaine / prilocaine cream. An hour later the test person returns for the same measurements described above (15 minutes).
- 3) At the end of the measurements described under 2) an 8% capsaicin patch is applied to the middle finger tip. After an hour the researcher comes along and the plaster is removed. A week later the test person returns to undergo the measurements as described under 1) again (15 minutes).

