7. STATISTICAL ANALYSIS

7.1 Primary study parameter(s)

-corelation coefficients between stimulus strength and AFI signal amplitude will be calculated. The statistical significance of the correlation will be calculated using linear regression analysis.

-repeated-measures ANOVAs will be performed between baseline recordings and recordings 1 hour after application of lidocaine/prilocaine cream and between baseline recordings and recordings 1 week after application of a capsaicin patch. Finally, a paired t-test will be used to compare 1.0mA, 5Hz and 1.0mA, 2000Hz electrical stimulation.

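### The sole objective asks for a reproducible signal, but no main parameter or planned analysis estimates agreement between repeated recordings under the same condition

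*Protocol*

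**What the plan says.** The Primary Objective under OBJECTIVES is the only objective: "we want to investigate whether a reproducible and validated flavoprotein signal can be obtained at the second fingertip of healthy subjects". The Summary repeats it ("whether a reproducible and validated flavoprotein signal can be obtained at the middle finger tip of healthy subjects"), and the Introduction gives a close variant: "we want to examine in healthy volunteers whether a reproducible and reliable AFI signal can be obtained after nociceptive stimulation in the epidermis".

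The five Study Design aims are a time relationship, linearity ("studying whether there is a linear relationship between the strength of the applied electrical signal and the size of the optical (flavoprotein) signal"), wavelength specificity, block by the cream and block by the capsaicin patch. Section 5.9.1 lists three main parameters: "magnitude and time course of the flavoprotein response", linearity, and block. Sections 5.9.2, 5.9.3, 7.2 and 7.3 (secondary and other parameters and their analyses) are marked not applicable.

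Section 5.11 duplicates the 5 Hz stimuli: "Each stimulus strength (0.5, 0.6, 0.7, 0.8, 0.9 and 1.0 mA) will be administered twice". It adds a pain rule: "The stimulus is interrupted when the pain intensity exceeds 7". The series is run untreated, then an hour after the cream, then a week after the patch.

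Section 7.1 plans three things: correlation and linear regression ("corelation coefficients between stimulus strength and AFI signal amplitude will be calculated"), repeated-measures ANOVAs of baseline against each treated session, and a paired t-test of 5 Hz against 2000 Hz at 1.0 mA.

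**The concern.** The objective has two halves. Linearity, block and the 2000 Hz control all serve validation. Nothing listed reports agreement between repeats, although the design produces the repeats. The protocol names its own main parameters and tests and closes the remaining slots, so this is a mismatch between objective and endpoints within one document. It is more than detail that a statistical analysis plan would supply.

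If the plan is followed as written, the report can present a slope, a correlation and a block effect without saying how far apart two recordings under identical conditions tend to be. Half of the objective is then unanswered, or is answered with a measure chosen after the data are seen. Section 2.4 says the results will be used to size a follow-up study, for which measurement error is a natural input.

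**Working it through.** **Is there a figure to reproduce?** No. Section 2.4 gives no sample-size calculation, SD or effect size. Every SD below is therefore an assumption.

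**Number of pairs.** 10 subjects × 6 strengths = 60 untreated duplicate pairs (120 recordings at 5 Hz) in the first session. This is an upper figure for 10 subjects, because interrupted stimuli leave incomplete pairs.

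**Do the planned outputs stand in for agreement?** Scale stimulus strength to x = 0, 0.2, …, 1, and let the mean response rise linearly by 1 from 0.5 to 1.0 mA. Let s be the within-subject SD of a single recording.

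- Repeatability coefficient (the difference that about 95% of repeat pairs stay within) = 1.96 × √2 × s.
- Over the six strengths Σ(x − x̄)² = 0.7. With two recordings at each strength this is 1.4 per subject, and 14 over 10 subjects.
- Subject-adjusted common slope: noncentrality √14 / s, with 120 − 10 − 1 = 109 df.
- Separate regression per subject: noncentrality √1.4 / s, with 12 − 2 = 10 df.
- Pooled regression ignoring subject: by simulation, between-subject SD 1.

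All tests are two-sided at 5%, which is also an assumption.

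| Assumed s (rise = 1) | Repeatability coefficient | Significant, subject-adjusted | Significant, pooled | Subjects significant, separate regressions | Mean per-subject r |
|---|---|---|---|---|---|
| 0.5 | 1.4 | >99.9% | 99.5% | 57% | 0.58 |
| 1.0 | 2.8 | 96% | 83% | 19% | 0.33 |
| 1.5 | 4.2 | 70% | 55% | 11% | 0.23 |

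So significance and r both respond to repeat error. How visibly they do so depends on the model, and section 7.1 does not say whether coefficients are pooled or per subject. The subject-adjusted column also assumes equal slopes. If subject slopes vary with SD 1 at s = 1.0, a test of the mean slope is significant in about 59% of trials and the pooled test in about 69%.

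**Does r isolate repeat error?** No, because it also falls with non-linearity. A plateau response 0, 1, 1, 1, 1, 1 with no repeat error gives Sxy = 0.5, Sxx = 0.7 and Syy = 5/6, so r = 0.5 / √(0.7 × 0.833) = 0.65. A linear response with s = 0.42 also gives a mean r of 0.65, yet its repeatability coefficient is 1.96 × √2 × 0.42 = 1.16. The first case is perfectly repeatable. In the second, repeats could differ by more than the whole rise. Duplicate differences separate the two; r does not.

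**What could the existing pairs deliver?** The 95% limits for an SD on ν df are the estimate times √(ν/χ²₀.₉₇₅) and √(ν/χ²₀.₀₂₅):

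| Pairs | Lower factor | Upper factor |
|---|---|---|
| 60 | 0.85 | 1.22 |
| 50 | 0.84 | 1.24 |
| 40 | 0.82 | 1.28 |
| 10 (one strength only) | 0.70 | 1.75 |

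These limits assume the same repeat SD in every subject and at every strength. If the log repeat SD varies between subjects with SD 0.2 or 0.3, coverage of the 60-df limits falls from 95% to 87% or 78%.

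**The case against.** *The duplicates are used.* A reader might infer that the paired recordings serve no purpose. Section 7.1 does not support that: they enter the regression and supply the baseline side of the ANOVAs. What is missing is a comparison within pairs.

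*The planned tests would expose a poor signal.* This stands in part. A reader might infer from the 96% figure that the analysis would nearly always hide poor repeatability, but that figure needs a subject-adjusted model with equal slopes, which section 7.1 does not specify. On separate regressions only about 19% of subjects would be significant, and the trouble would usually show. It would show as non-significance, though, which does not measure agreement and does not tell repeat error from non-linearity or a weak response.

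*Reproducible may mean that the response appears consistently across subjects.* The protocol does not define the word, so this is possible, and magnitude and time course in 10 subjects bear on it. Even so, neither 5.9.1 nor 7.1 names a measure of that consistency, and the pairing with reliable in the Introduction makes agreement on repetition a natural reading.

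*Handling of duplicates belongs in an analysis plan.* This is fair for averaging rules and the choice of coefficient. It does not cover a named half of the only objective that has no parameter or analysis in the document that lists them.

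*The remedy is limited.* Also fair. The pairs are clustered in 10 subjects, interrupted stimuli may remove pairs where pain is highest, and without a threshold the judgement stays partly open. These points limit the conclusion but leave the gap in place.

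**Conclusion.** The point holds in this form: the only objective includes reproducibility, and no main parameter or planned analysis estimates agreement between repeated recordings under the same condition. On no reading of section 7.1 is an agreement estimate a stated output. That conclusion comes from the text and does not depend on the simulation. The illustration (repeatability coefficient 2.8 times the rise, with slope significance of 96%, 83% or 19% depending on the model) rests on assumed SDs and a linear response.

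A reader might also infer that the data cannot answer the question, or that the validation half is unsupported too. Neither follows. Up to 60 untreated pairs are planned and none is lost, and linearity, block and the 2000 Hz control address validation. The pairs do speak only to within-session repeatability, because both later sessions follow the cream or the patch. The gap should be fixed before analysis.

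**What to change.** 1. Add to 5.9.1: within-session repeatability of the AFI amplitude, from the 5 Hz duplicates of the first session, before the cream.
2. Add to 7.1: the within-subject SD, estimated as √(Σd² / 2m) from the m duplicate differences d pooled over strengths, and the repeatability coefficient 1.96 × √2 × SD. Give a 95% CI that allows for clustering in 10 subjects, for example a bootstrap by subject, or show the per-subject SDs. Report the number of complete pairs per strength (both 10-second stimuli completed), and set the result beside the mean 1.0 mA response with its CI.
3. State that the conclusion on reproducibility rests on this estimate, not on the slope p-value or r, and covers within-session repeatability only. A numerical acceptance threshold is optional and for the sponsor to choose, since section 2.4 says no prior data exist.

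Alternatively, remove the word reproducible from the objective wherever it appears.

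Cost: one line in 5.9.1, a few in 7.1 and one extra analysis, with no new subjects or recordings. Between-session reproducibility stays unanswered.

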2. STUDY POPULATION

2.1 Population (base)

2.2 Inclusion criteria

In order to be eligible to participate in this study, a subject must meet all of the following criteria:

-10 healthy volunteers

2.3 Exclusion criteria

A potential subject who meets any of the following criteria will be excluded from participation in this study:

-younger than 18 years

-ready existing neuropathy

-allergy to local anaesthetics

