5.4 Summary of known and potential risks and benefits

-EMLA 5% (from SmPC) Common (>1/100): Transient local reactions at the application site such as paleness, erythema (redness) and oedema. An initial and usually mild sensation of burning, itching or warmth at the application site. Uncommon (1/1000 to 1/100): An initial mild burning, itching sensation or warmth at the application site; local paresthesia at the application site, e.g. tingling sensation; and skin irritation at the application site. Rare (<1/1000): Methaemoglobinaemia (especially at longer application time in children with atopic dermatitis or mollusca contagiosa). Corneal irritation after accidental eye exposure.

-Qutenza 8% patch: On application a sensation of prickling and/or burning will occur for approximately 180 minutes, together with an area of erythema of the skin. In case of severe pain, a cold pack can be applied to the site of application to reduce pain, and oral analgesics, such as paracetamol, can also be provided. Hypersensitivity to pressure and heat can occur for up to two days. As with any medication, rare side effects cannot be excluded beforehand.

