5.5 Description and justification of route of administration and dosage

- the route and dosage of lidocaine/prilocaine and the capsaicin patch is being used according to the SmPCs of lidocaine/prilocaine and the capsaicin patch.
- studies using cutaneous capsaicin patch 8% have demonstrated that this regimen is suitable to cause epidermal denervation in healthy subjects (10).

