5.6 Dosages, dosage modifications and method of administration

- the route and dosage of lidocaine/prilocaine and the capsaicin patch is being used according to the SmPCs of lidocaine/prilocaine and the capsaicin patch.
- a small patch of 8% capsaicin will be applied to the middle finger for 60 minutes.

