10. STRUCTURED RISK ANALYSIS

10.1 Potential issues of concern

a. Level of knowledge about mechanism or action

-for lidocaine / prilocaine cream and capsaicin 8% patches see section 5.2

With regard to the safety of the neurometer: the electrical stimulus is generated by a low voltage source, or a battery. For safety reasons, the Neurometer is constructed in such a way that it does not generate a stimulus when it is connected to the mains.

b. Previous exposure of human beings with the test product (s) and / or products with a similar biological mechanism

-for lidocaine / prilocaine cream and capsaicin 8% patches see section 5.2

- as far as we know, there have never been safety incidents with a Neurometer

c. Can the primary or secondary mechanism be induced in animals and / or in ex-vivo human cell material?

Yes, but the purpose of the above pilot study is to see if the AFI method is applicable to people. This method has already been applied to rats (7).

d. Selectivity of the mechanism to target tissue in animals and / or human beings

No, see above

e. Analysis of potential effect

Because lidocaine / prilocaine cream and capsaicin 8% patches are both already registered drugs, although not registered for use in healthy volunteers, but in patients prior to surgery or in patients with neuropathic pain, these drugs are safe at the dose used and there are no serious side effects to be expected.

f. Pharmacokinetic considerations

for this we refer to section 5.2 (SPC forms)

g. Study population

10 healthy volunteers

h. Interaction with other products

none, because both lidocaine / prilocaine cream and the capsaicin 8% patches only work locally on the skin

i. Predictability of effect

does not apply

j. Can effects be managed?

Lidocaine / prilocaine cream is a negative control experiment in the pilot study, but also serves to prevent the acute burning pain after administration of the capsaicin patch.

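### The exclusion criteria screen for allergy to the anaesthetic cream but not to the capsaicin 8% patch that every volunteer also receives

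*Protocol*

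**What the plan says.** Section 2.3 of the protocol lists three exclusions: age under 18, existing neuropathy, and "allergy to local anaesthetics". The only inclusion criterion (section 2.2) is being a healthy volunteer, and the term is not defined.

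Section 5.1 names two products, lidocaine/prilocaine cream and a capsaicin 8% patch. Section 5.11 begins "Each subject will undergo a series of electrical stimuli", applies the cream in step 2, and in step 3 says that "an 8% capsaicin patch is applied to the middle finger tip". Section 5.6 gives the exposure: "a small patch of 8% capsaicin will be applied to the middle finger for 60 minutes". Randomisation and allocation are marked not applicable (section 5.10).

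Section 5.4 describes local reactions for both products. For the cream it lists "Transient local reactions at the application site such as paleness, erythema (redness) and oedema". For the patch it describes prickling or burning "together with an area of erythema of the skin". Section 10.1(e) says of both drugs that they are registered, "although not registered for use in healthy volunteers".

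**The concern.** The protocol treats allergy to an applied product as a reason to keep someone out, but does so for only one of the two products. A recruiter who follows section 2.3 to the letter could enrol a person with a known capsaicin or patch allergy and apply the patch.

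What is at stake is the safety of that volunteer, not the validity of the results. Section 3.2 says that the products serve as negative controls and are not the aim of the study. The volunteer therefore gains nothing therapeutic that could offset a reaction which one question at screening would avoid.

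**Working it through.** There is no figure to reproduce. The check sets the eligibility list beside the exposures and then asks whether any other section closes the gap.

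**Exposure against exclusion**

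| Product (section 5.1) | Given to whom (section 5.11) | Allergy exclusion (section 2.3) |
|---|---|---|
| Lidocaine/prilocaine cream | every subject, step 2 | yes |
| Capsaicin 8% patch | every subject, step 3 | none |

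Products applied: 2. Products with an allergy exclusion: 1. Not covered: 2 − 1 = 1, the patch. Section 5.11 names no subset and section 5.10 provides no allocation, so all 10 planned volunteers are to receive both.

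**Does the risk section explain the difference?** No. Section 5.4 gives local reactions for both products and mentions allergy for neither. It expects no less discomfort from the patch: about 180 minutes of burning, with hypersensitivity to pressure and heat for up to two days.

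**Does the reference to the product information close the gap?** No.
- Sections 5.2 and 5.3 cite the texts for non-clinical and clinical findings.
- Section 5.5, repeated in 5.6, adopts them for a limited purpose: "the route and dosage of lidocaine/prilocaine and the capsaicin patch is being used according to the SmPCs".
- Section 10.1 points back to them for mechanism, previous human exposure and pharmacokinetics.

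None of these makes a contraindication an eligibility rule.

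**Does another safeguard screen before exposure?** None that is written down.
- Being healthy is undefined, and a healthy adult can have a contact allergy. The separate anaesthetic exclusion suggests that the authors did not rely on the word to deal with allergy.
- Section 5.8 concerns dispensing and accountability, not allergy.
- Specific withdrawal criteria are marked not applicable (section 5.12.1).
- Withdrawal for urgent medical reasons (section 5.12) and the recording and follow-up of adverse events (sections 6.2.1 and 6.4) are not allergy screens. In practice they respond to a reaction once it has occurred.

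**The case against.** The strongest reply is that this is a suggestion to lengthen a list, not an error. Nothing in the protocol contradicts section 2.3, and no rule in it says that each applied product needs its own allergy exclusion. The anaesthetic may have been singled out because section 10.1(j) gives the cream a second role, preventing the acute burning from the patch. The protocol documents no case or frequency of patch allergy. Practical safeguards also exist: volunteers receive an information form and have a week to consider (section 8.3), the investigator can withdraw a subject, and section 10.1(e) expects no serious side effects. A volunteer who knows of an allergy would probably say so, and section 5.13 provides for replacement.

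Much of this stands. The list is incomplete rather than contradictory, the hazard cannot be quantified from the protocol, and the likely harm is small. The information form is not available here and may prompt a volunteer to decline.

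It does not remove the gap. The cream's second role is a possible motive that the protocol does not state, and it would not be a reason to leave the patch out. Relying on a volunteer to speak up is not screening. Nor does the point depend on the patch's product information: not applying a product to someone known to be allergic to it is the same reasoning that the protocol already uses for the cream.

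**Conclusion.** The concern holds as a minor gap in eligibility. As written, a volunteer with a known capsaicin or patch allergy qualifies and would receive the patch. One of the two applied products has no allergy exclusion, and all 10 planned volunteers are to receive both.

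No probability or expected number of reactions is claimed, because the protocol gives no frequency. Exposure is limited to one small fingertip patch for 60 minutes. No endpoint, analysis or stated figure is affected. The conclusion rests on the protocol text alone, and on the assumption that no screening document outside it already asks the question. It merits consideration as a cheap safety improvement, not a change to the design.

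**What to change.** Extend the third exclusion in section 2.3 to read: *known allergy or hypersensitivity to local anaesthetics, or to capsaicin or any component of the patch*. Check it with one question at screening.

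The cost is one phrase and one question. A volunteer may, rarely, be screened out.
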